Test plan
Clinical trial of two fissure sealants -

Version 3.0

September 01, 2021

Synopsis

Title:	Clinical trial of two fissure sealants
Testing institute:	1. Polyclinic for Conservative Dentistry and Periodontology, LMU Munich, Munich (Germany) 2. [name] Dental Practice, [name] (Switzerland)
Sponsor:	Ivoclar Vivadent AG, [name] (Liechtenstein)
Clinical indication:	Fissure sealing for caries prevention in children and adolescents
Aim of the study:	Comparison of two different fissure sealants
Target criteria: Primary endpoint:	Retention rate of the applied fissure sealants
Secondary endpoints:	Occurrence of caries
Study design:	Two-center, randomized, prospective, blinded study in a "split-mouth" design
Test products	The medical devices to be tested (Helioseal F and Helioseal F Plus) are assigned to class IIa. CE marking is available.
Treatment plan:	Sealing of at least one pair of teeth per test subject Follow-up after 7-28 days, 6 months, 1 year, 2 years, 3 years
Selection of patients	From the patient pool of the trial centers
Inclusion criteria	
Inclusion criteria for a patient
 
 - Indication for sealing the fissures - ASA status 1 - All dentin lesions in need of restoration have been repaired - Consent of the parents and the patient - Detailed instruction and demonstration of age-appropriate oral hygiene, accompanying prevention concept. - Age: 5-13 years (Wädenswil) - Age: 5-18 years (Munich) 
Inclusion criteria for tooth pair to be sealed
 
 - 1st or 2nd permanent molars

Exclusion criteria	
Exclusion criteria for a patient
 
 - No consent of the parents / patient - Allergy and known intolerance reactions to methacrylates or other components of dental sealing/restorative materials 
Exclusion criteria for tooth pair to be sealed
 
 - Molars with clinical cavitations on the occlusal surface (UniVISS occlusal score $\geq M$) - molars with untreated dentin lesions according to the clinical examination. If necessary, a bitewing radiograph is indicated. - Premolars, permanent anterior teeth with sealable pits, deciduous molars - Extensively restored teeth where sealable parts of the occlusal surface are included in the restoration. - - Teeth with hypomineralization or other structural disorders or shape anomalies
Methodology:	
 - Cleaning the tooth surfaces and fissures with cleaning paste (Proxyt green) and a rotating brush - Removal of paste residues by water rinsing - Blow the tooth surface dry well with a strong stream of air - Relative draining (LMU Munich) / rubber dam ([name] dental practice) - Conditioning with a 37% phosphoric acid etching gel - Sealing of fissures and pits 
 o Test group: Helioseal F Plus o Control group: Helioseal F

Statistical analysis	
The retention of the fissure sealants used is analyzed using survival curves (Kaplan-Meier), with the proportion of intact fissure sealants serving as the primary endpoint. Caries infestation and incidence serve as secondary endpoints. The study design was chosen to test for non-inferiority of the newly developed sealant (Helioseal F Plus).
 
The nQuery Advisor 6.0 program (Statistical Solutions, Saugus, MA, USA) was used to estimate the number of cases and a scenario for the non-inferiority of two fissure sealing techniques was calculated. The underlying assumptions are:
 
The underlying assumptions are:
 
 - Study objective: To demonstrate the non-inferiority of the experimental therapy compared to the established standard therapy - Main outcome measure: Proportion of intact fissure sealings - Conjoined samples (split-mouth design) - Alpha level: 5% (two-sided) - Power: 80% $n_a = n_b = \left(\frac{p_a(1-p_a)}{k} + p_b(1-p_b) \right) \left(\frac{z_{1-\alpha/2} + z_{1-\beta}}{p_a - p_b - \delta} \right)^2,$ 
N= 55 pairs of teeth per group
 
As a result of the case number estimation, 55 pairs of teeth per site should be included. Due to an expected drop-out of about 10%, additional patients must be included, so that a number of 61 tooth pairs per group and 122 in total seems appropriate. Therefore, at least 120 pairs of teeth are planned at the start of the study, with at least 60 pairs of teeth to be sealed in each study center.

number of patients:	120 pairs of teeth (60 per study location)
Schedule:	
Recruitment: Following approval (from the end of Q2 2018) Baseline examination & sealing (T0; from the end of Q2 2018) Follow-up examination I 7-28 days after T0 Follow-up II 6 ± 1 months after T0 Follow-up III 12 ± 2 months after T0 Follow-up IV 24 ± 2 months after T0 Follow-up V 36 ± 2 months after T0

Risk category according to Art. 20 ClinO	Category A

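### The sample size assumes paired teeth but uses a formula for independent proportions, and no variance is named for a non-inferiority comparison in which a child may contribute several tooth pairs

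*Combined protocol and SAP*

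**What the plan says.** The Statistical analysis row of the Synopsis gives the objective: "To demonstrate the non-inferiority of the experimental therapy compared to the established standard therapy". The outcome is a proportion ("Main outcome measure: Proportion of intact fissure sealings"), and the sampling assumption is "Conjoined samples (split-mouth design". Alpha is 5% two-sided and power is 80%.

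The formula printed beneath these assumptions has the variance term p_a(1-p_a)/k + p_b(1-p_b). The symbols p_a, p_b, delta and k are given no values. The result is 55 tooth pairs, described as per group in one sentence and per site in the next. After dropout the text says "a number of 61 tooth pairs per group and 122 in total seems appropriate". The number-of-patients row reads "120 pairs of teeth (60 per study location"; the number of children is not stated.

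The Treatment plan row specifies "Sealing of at least one pair of teeth per test subject". The inclusion criteria admit first and second permanent molars, so up to eight teeth, or four pairs, per child.

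On analysis, retention "is analyzed using survival curves (Kaplan-Meier), with the proportion of intact fissure sealants serving as the primary endpoint". The same row adds that "The study design was chosen to test for non-inferiority of the newly developed sealant". It gives no test, confidence interval, standard error, or paired or clustered method.

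**The concern.** A non-inferiority conclusion rests on a confidence limit for the test-minus-control difference, and so on its standard error. Two features of this design affect that standard error. Teeth are matched within a pair, and pairs can be nested within a child. Positive correlation within a pair makes an independent-samples interval too wide. Positive correlation of the pair differences within a child makes it too narrow.

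The printed formula reflects neither feature, although pairing is one of its stated assumptions. The analysis text does not say how either will be handled. The usual Kaplan-Meier (Greenwood) variance treats every tooth as an independent unit. If an analyst fell back on it, the one-sided error would no longer be tied to the nominal 2.5%. The Kaplan-Meier point estimates are not in question.

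**Working it through.** **1. The plan's own figure.** With p_a = p_b = p, k = 1, one-sided 0.025 and 80% power, the printed formula is n = 2p(1-p)(1.960 + 0.842)²/delta². It cannot be run forwards because p and delta have no values. Solved backwards for n = 55, it gives a delta of 0.245 at p = 0.70, 0.214 at 0.80, 0.160 at 0.90 and 0.116 at 0.95. None of these combinations appears in the plan. For dropout, 55 × 1.1 = 60.5, which rounds to 61 (55/0.9 = 61.1), and 2 × 61 = 122. Taking 10% from the planned 120 pairs leaves 108.

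**2. What the formula omits** (correlations assumed; 55 taken as the independent-samples result).
- Pairing: with equal rates the variance becomes 2p(1-p)(1-rho), so the need is 55(1-rho). That is 50, 44, 39 and 28 pairs at rho = 0.1, 0.2, 0.3 and 0.5.
- Several pairs per child: the need is 55[1 + (m-1)ICC], where ICC refers to the pair differences. With m = 2 it is 61 (ICC 0.1) or 72 (ICC 0.3); with m = 4 it is 72 or 105.

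The two omissions act in opposite directions.

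**3. Effect on the one-sided error** (simulation; retention level and correlations all assumed). The model is logistic with intercept 2.0. The child effect has SD 0.5, 1 or 2 on the log-odds scale. The child-by-treatment effect has SD 0, 0.5, 1 or 2 and is split equally between the sealants, so the true difference is 0. Retention comes out at 76-87%. There are 108 pairs in four layouts: 1, 2 or 4 pairs per child (108, 54 or 27 children), and a mixed layout of 34 children with 1 pair, 27 with 2 and 5 with 4 (34 + 54 + 20 = 108 pairs, 66 children). That makes 48 settings.

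The naive variance is [p_t(1-p_t) + p_c(1-p_c)]/n, to which Greenwood reduces without censoring. The clustered variance sums the pair residuals within each child, squares and adds these sums, multiplies by K/(K-1) and divides by n², where K is the number of children. At 6,000 runs the Monte Carlo standard error near 2.5% is about √(0.05 × 0.95/6000)/2 = 0.14 percentage points, so the ends of each range can move by a few tenths.

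| One-sided error, target 2.5% | 1 pair | 2 pairs | 4 pairs | mixed |
|---|---|---|---|---|
| Naive; child SD 0.5-1, child-by-treatment SD 0-1 | 1.9-2.6% | 1.8-3.0% | 1.7-3.8% | 1.9-3.0% |
| Naive; child SD 0.5-1, child-by-treatment SD 2 | 2.5-3.0% | 4.1-4.5% | 6.4-7.3% | 3.9-4.7% |
| Naive; both SDs 2 | 1.3% | 2.3% | 4.7% | 2.7% |

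With child SD 2 and child-by-treatment SD 0-1, the naive error is 0.7-1.9% over all layouts. The clustered limit with t on K-1 degrees of freedom gives 2.2-2.9% over all 48 settings.

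**4. Power of a clustered analysis at 108 pairs.** Let f be the true variance divided by the naive variance. The simulated ratios of naive standard error to true SD run from 0.755 to 1.248, so f runs from 1/1.248² = 0.64 to 1/0.755² = 1.75. Power = Phi(2.8016 × √(108/N)/√f - 1.960), where N is the total number of pairs needed for 80% power under independence.
- N = 55: 99.8% at f = 0.64, 97.5% at f = 1, 84.2% at f = 1.75.
- N = 110 (55 needed at each site): 2.8016 × √(108/110) = 2.776. This gives Phi(2.776/0.800 - 1.960) = 93.4% at f = 0.64, 79.3% at f = 1, and Phi(2.776/1.323 - 1.960) = 55.5% at f = 1.75.

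**The case against.** Four points can be made on the other side.

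- **The formula is conservative for pairing.** With positive within-pair correlation it asks for more pairs than needed, so using it as an approximation could be largely a matter of labelling. This stands for pairing alone. It does not cover several pairs per child, and the plan does not call the formula an approximation.

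- **No wrong variance has been specified.** This stands. The plan names no standard error, and its paired assumption is at least as compatible with a paired analysis. A reader might infer that a naive interval is planned; the text does not say so. What is established is a gap, and the naive limit is only what a default would give.

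- **The effect is small.** In ordinary settings it is. The figure near 7% needs a child-by-treatment SD of 2 and all eight first and second molars eligible in every child. That is implausible with a lower age limit of 5 and the tooth-level exclusions. The simulation also has complete binary outcomes, so censoring over 36 months is untested.

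- **The step from 61 to 122 is coherent.** A reader might take the doubling as proof that the arms were treated as separate samples, because 61 split-mouth pairs already put 61 teeth in each arm. The documents do not support that. If group means site, then 55 per site, 61 after dropout, 122 for two sites and 60 per location fit together. The wording is ambiguous, but it does not show how 55 was derived.

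The text available is a synopsis and brief by nature. It nevertheless contains the sample-size argument and names the analysis, and the mismatch between assumption and formula lies within one row.

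**Conclusion.** The point holds as an inconsistency and an omission. The formula does not match its own paired assumption, and the plan leaves open the variance on which the non-inferiority conclusion depends while allowing an unlimited number of pairs per child. If the default Kaplan-Meier variance were used, the departure from 2.5% would probably be modest, and its direction cannot be determined from the plan. All the error figures rest on assumed retention and correlations.

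A reader might infer that the trial is too small. The documents do not show this: the rates and margin behind 55 are not given, and pairing and clustering pull in opposite directions. Power at 108 evaluable pairs is about 84-99.8% if 55 is the total need. If 55 is needed per site, or 110 in total, it is about 56-93%, and 79% with no pairing or clustering effect. The plan does not say which applies.

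**What to change.** - Base the non-inferiority confidence limit for the test-minus-control retention difference on within-pair differences, with variance clustered on the child. Suitable forms are a paired risk difference or GEE with robust variance and a t reference on the number of children, or a bootstrap of the Kaplan-Meier difference that resamples whole children.
- Report the number of children and the distribution of pairs per child.
- Replace the printed formula with a paired one, or label it an independent-samples approximation that allows for neither pairing nor several pairs per child. Restate the power on that basis, with the values used for p_a, p_b and delta.
- State whether 55 and 61 are per site or in total.

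The cost is revised wording, a standard software option, and a child identifier on every tooth pair in the analysis data. No extra enrolment or visits are needed. The downside is that the interval may widen if many children supply several pairs.

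### Does leaving the read-out visit for the proportion of intact sealants unnamed leave the non-inferiority verdict open?

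*Combined protocol and SAP*

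**What the plan says.** All the text supplied is a synopsis. Under Target criteria the primary endpoint is "Retention rate of the applied fissure sealants", with no time attached. The Treatment plan row lists "Follow-up after 7-28 days, 6 months, 1 year, 2 years, 3 years", and the Schedule row ends with "Follow-up V 36 ± 2 months after T0".

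The Statistical analysis row says that retention "is analyzed using survival curves (Kaplan-Meier), with the proportion of intact fissure sealants serving as the primary endpoint", and that the design tests non-inferiority of the newer sealant. The sample-size assumptions name the outcome, "Main outcome measure: Proportion of intact fissure sealings", a two-sided 5% alpha and 80% power. They then print a formula for two proportions and the result, "N= 55 pairs of teeth per group". The formula's p_a, p_b and delta have no numerical values. No visit is marked as primary, and nothing says how a loss found at a visit is dated for the curve.

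The title block is dated "September 01, 2021". The Schedule row has "Baseline examination & sealing (T0; from the end of Q2 2018".

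**The concern.** A proportion intact exists only at a stated time. A non-inferiority test of two proportions with a single margin therefore needs a time at which they are compared. Kaplan-Meier does not remove that need, because the plan gives no whole-curve measure, such as a hazard ratio with its own margin.

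The true difference between two sealants starts near zero and may widen, or widen and then close. One margin can therefore give different answers at months 12, 24 and 36. The sample size does not show which visit was meant, since the rates and margin behind it are not given.

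The dates sharpen the point. On the plan's windows, a child sealed on 30 June 2018 would finish the 36-month visit by the end of August 2021, just before the version date. If the visit were chosen after results were known, the choice could decide the verdict. A second, smaller worry is that dating losses at the actual examination, within a window of ±2 months, could shift the curve near month 36.

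**Working it through.** **The plan's own figure.** N = 55 cannot be computed forwards, because p_a, p_b and delta have no values. With k = 1 and equal true rates p, the printed formula can be solved for the margin:

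delta = √(2p(1−p)/55) × (1.960 + 0.842)

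- p = 95%: √(0.095/55) × 2.802 = 11.6 points
- p = 90%: √(0.18/55) × 2.802 = 16.0 points
- p = 80%: √(0.32/55) × 2.802 = 21.4 points

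The sample size fits many pairs of rate and margin, so it does not reveal the visit.

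**How far the verdict moves with the visit.** Everything in this step is assumed except the visit times, the alpha and the 10% drop-out. Control retention is 90% at month 36. The margin is the implied 16.0 points, and the test sealant sits exactly on it at 74.0%. Loss is constant, so retention at month t is p36^(t/36). There are 108 pairs (120 less 10%). Non-inferiority is declared if the lower limit of the paired Wald 95% interval is above −16.0 points. Results are from 10,000 simulated trials per scenario, with within-mouth latent correlation 0 and 0.4.

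| Month | Control | Test | True gap (points) | Declared non-inferior |
|---|---|---|---|---|
| 12 | 96.5% | 90.4% | 6.1 | 83-87% |
| 24 | 93.2% | 81.8% | 11.4 | 20-23% |
| 36 | 90.0% | 74.0% | 16.0 | 2.8-3.0% |

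A hand check at month 12 with independent teeth: SE = √((0.9655×0.0345 + 0.9044×0.0956)/108) = 0.0333, and (0.1603 − 0.0611)/0.0333 − 1.96 = 1.02. The normal probability is about 85%, in line with the simulation.

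**Sensitivity to the number of pairs.** The Statistical analysis row gives 55 pairs both per group and per site. With 55 pairs analysed instead of 108, the month-12 figure falls to about 59-63%. The direction is unchanged.

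**Month 36 alone.** With control retention of 80, 90 or 95%, Weibull shapes from 0.3 to 1.5 common to both sealants, and the test product on the implied margin, the month-36 rate is 2.3-3.8%. The nominal one-sided level is 2.5%. If the sealants are equal at every visit and the margin is the implied one, non-inferiority is declared in 97-100% of trials whichever visit is used.

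**Dating of losses.** Take a true 90% v 80% at month 36, constant loss, no drop-out, and losses dated at the examination. Last visits spread evenly over months 34-38 and read at month 36 give a gap of 8.9 points instead of 10. Narrower or shifted last-visit ranges give 8.1 to 11.2. The proportion intact at visit V gives 9.8-10.1 in every case. In a separate worked data set of 110 pairs, dating at the visit and dating at the interval midpoint gave the same Kaplan-Meier difference, −6.9 points, when read at month 36.

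**The case for a change.** The strongest reply is that month 36 is only the natural choice and the text never says so. An unstated default does not bind anyone, and a version dated about three years after the planned start of sealing leaves room to choose with data in hand. Nor is the sensitivity confined to a product on the margin. With equal sealants and an assumed margin of 10 or 15 points, under assumed retention of 90, 80 and 70% at months 12, 24 and 36, the verdicts at those visits disagree in about 20-50% of trials. The visit can cut the other way too. If the test sealant loses early and the control late, both reaching 80% at month 36, the pass rate with a 21.4-point margin is 77% at month 12 and 98% at month 36.

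It stands that the supplied text names no visit, and that one sentence naming it would do no harm. The rest carries less weight. The high pass rate at month 12 is a correct answer to a different question, because the true gap then is 6.1 points and inside the margin. Every verdict figure depends on invented rates and margins. The missing p_a, p_b and delta are a separate gap, and naming a visit would not fill it. The Schedule row gives a planned start and does not record when sealing began. Nothing shows that anyone had seen outcome data, and the study is described as blinded. The text is also a synopsis, where this level of detail is often left out.

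**Conclusion.** No change is needed. The omission is real, but it is a gap that a competent analyst fills in one way: the curves run to the last scheduled visit and the proportion intact is compared there. Under that reading, the error rate for a product exactly on the margin is 2.3-3.8% in the common-pattern scenarios tried, and the proportion at visit V is within about 0.2 points of the truth. Using examination dates instead costs about one point with visits spread over the full ±2-month window (8.9 against 10), and up to about two in a skewed window (8.1).

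The large contrast, about 83-87% at month 12 against about 3% at month 36, arises only if an earlier visit is put forward as the primary result. It also assumes 90% v 74% retention, a 16.0-point margin carried to every visit, and 108 independent pairs. The documents give no sign that an earlier visit was intended or used. A reader of the results should expect the non-inferiority comparison at three years, and should ask why if it is reported at another visit.
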